02.05.2018

Title

Treatment of Newly Diagnosed Gastroesophageal Reflux Disease in a National Population-based Cohort

Aim

To compare rate of surgery with medical treatment in patients with newly diagnosed gastro-esophageal reflux disease in a nationwide population based cohort over 15 years.

Background

Episodic reflux of gastric contents to the esophagus is physiological but is considered gastroesophageal reflux disease (GERD) when accompanied by bothersome symptoms, typically heartburn, regurgitation or retrosternal pain. Extra-esophageal symptoms such as asthma, laryngitis and chronic cough may also occur (1). GERD is a complex and multifaceted disease (2, 3), affecting 10-20% of the Western population (4) and has been shown to significantly reduce the quality of life (5). Worldwide, the prevalence of GERD has been increasing (6–8). Treatment of GERD consists of anti-secretory drugs, mainly proton pump inhibitors (PPI), or anti-reflux surgery. Laparoscopic anti-reflux surgery is considered standard of care in surgical treatment of gastro-esophageal reflux disease (9) and with careful patient selection based on thorough preoperative workup (10), symptom control and patient satisfaction are high compared to medical therapy. This has previously been demonstrated in metaanalysis (11, 12).

From 1990-2000 the utilization of anti-reflux surgery in the USA rose to 16.7 procedures per 100.000 inhabitants with a concomitant rise in the use of the transabdominal laparoscopic approach. This resulted in a decline of perioperative mortality and morbidity (13, 14). The rate of anti-reflux surgery dropped to 6.1 procedures per 100.000 inhabitants in 2010, when the patients were now older with significantly higher levels of comorbidity. Despite this, length of stay, morbidity and mortality was reduced even further. The laparoscopic approach is used in 80% of American procedures and the rate has not changed during the last ten years. It is unknown whether Denmark follows the same trends, as the popularity of anti-reflux surgery has been somewhat limited and the surgical setup is different with significantly fewer centers. In a Danish study, investigating the rate of reoperative anti-reflux surgery from 1997-2005, the rate of primary surgery was 5.2 per 100.000 inhabitants with a reoperation rate of 5% (15), however no data has been presented after 2005, and no Danish study has focused on treatment of newly diagnosed patients suffering from reflux disease.

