As such, it is currently unknown how many patients each year are given the diagnosis GERD after upper endoscopy in Denmark and what treatment they receive. It is also unknown how the utilization of medical and surgical treatment has developed in this group of patients.

Methods

The study is a register-based cohort study with data from Danish national health registries (The National Patient Registry, The Danish National Prescription Register and The Civic Registry). The study period is 2000-2015.

The study population consists of all adult Danish patients diagnosed with GERD and GERD-related diagnosis identified with ICD-10 codes DK20.9B, DK21.0-21.9B & DK22.7 using The National Patient Registry).To

02.05.2018

validate GERD-diagnosis, upper endoscopy must have been performed no more than three months before time of diagnosis for the patient to be included. Endoscopy must have been performed during the study period 2000-2015.

Patients with GERD and GERD-related diagnosis up to four years before upper endoscopy are excluded from the study as are patients with any diagnosis of cancer of the gastrointestinal tract 4 years prior to upper endoscopy to the end of follow-up.

Age, sex and Charlson Comorbidity Index at date of primary upper endoscopy are derived from the National Patient Registry. From the same source, any anti-reflux surgery (Nomesco: KJBC00, KJBC01, KJBC02, KJBW96, KJBW97) performed within two years of inclusion are identified.

From The National Prescription Register, data on medical treatment with any antacid and anti-secretory treatment (ATC: MA02B) are identified from 4 years before inclusion to 2 years after. Data on anti-thrombotic drugs and non-steroid anti-inflammatory drugs (ATC: MB01A & MM01A) are also retrieved for the same period to adjust for possible preventive therapy with anti-secretory drugs. From the Civic Register, data on mortality in the follow-up period are retrieved.

Statistical analysis

Data will be analyzed using STATA15. Descriptive analysis of age, sex, Charlson Comorbidity Index, mortality and rate of anti-thrombotic treatment comparing patients treated pharmacologically (in defined daily dosages per year) or surgically (any anti-reflux procedure) for reflux disease using Student's t-test, Chi2-test and Mann-Whitney-U test.

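### The drug-versus-surgery mortality test may reward the group treated later: if groups are formed by treatment up to two years after inclusion and deaths are counted from inclusion, unequal waiting time alone can create a difference.

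*Combined protocol and SAP*

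**What the plan says.** The Statistical analysis section of the combined protocol and SAP opens with a "Descriptive analysis of age, sex, Charlson Comorbidity Index, mortality and rate of anti-thrombotic treatment". The same sentence sets drug-treated against surgically treated patients: "mortality and rate of anti-thrombotic treatment comparing patients treated pharmacologically (in defined daily dosages per year) or surgically (any anti-reflux procedure". The tests named are Student's t-test and the "Chi2-test and Mann-Whitney-U test". None of these adjusts for covariates or for time.

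The Methods section gives the data windows. Anti-reflux operations "performed within two years of inclusion are identified". Drug data "are identified from 4 years before inclusion to 2 years after". From the civil register, "data on mortality in the follow-up period are retrieved". The end of follow-up is mentioned once more, in the gastrointestinal cancer exclusion ("4 years prior to upper endoscopy to the end of follow-up"), and is not defined there either.

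The plan states no time zero for mortality, no landmark, no person-time rate and no time-dependent treatment variable. It has no rule for patients who receive both drugs and surgery. The one Cox model has time to starting treatment as its outcome, not death. The Aim is "To compare rate of surgery with medical treatment in patients with newly diagnosed gastro-esophageal reflux disease"; mortality is not part of it.

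**The concern.** Age, sex and the Charlson index are fixed at the primary endoscopy and cannot be altered by later treatment. Mortality can act on group membership itself. Someone who dies in the first month cannot be operated on in the ninth and so can never appear as a surgical death. If groups are formed by looking forward from inclusion, and deaths are counted from inclusion, each group's mortality is lowered by the time its members had to survive before treatment. If that time is the same in both groups, the effect cancels. If it differs, the group treated later looks healthier even when treatment does nothing.

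At stake is a p-value for drug versus surgical mortality that may reflect waiting time alone and that readers could take as a survival difference.

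**Working it through.** The plan states no sample size, mortality rate, treatment timing or alpha, so it has no figure to reproduce. The check asks what the planned comparison returns when treatment has no effect.

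**Inputs**
- From Methods: surgery counts up to 2 years after inclusion, and drug data also run to 2 years after.
- Assumed: those windows define disjoint groups; deaths are counted from inclusion; constant death rate λ = 0.02 per year in both groups; drugs start uniformly over 0–0.25 years; surgery starts uniformly over 0–2, 0–1 or 0.25–1 years; follow-up T is 2, 5 or 10 years.

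**Formula.** For treatment starting uniformly on (a, b), the mean survival to treatment is m = [exp(−λa) − exp(−λb)] / [λ(b − a)]. Then P(death by T | treated) = 1 − exp(−λT)/m.

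**Worked case (T = 2, surgery over 0–2 years).**
- exp(−0.04) = 0.96079.
- Drugs: m = 0.99750, risk = 1 − 0.96079/0.99750 = 0.0368.
- Surgery: m = 0.98026, risk = 1 − 0.96079/0.98026 = 0.0199.
- Risk ratio = 0.0199/0.0368 = 0.54.

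**Risk ratio, surgical to drug**

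| Surgery timing | 2 years | 5 years | 10 years |
|---|---|---|---|
| 0–2 years | 0.540 | 0.828 | 0.919 |
| 0–1 year | 0.803 | 0.927 | 0.966 |
| 3–12 months | 0.737 | 0.902 | 0.954 |
| same as drugs | 1.000 | 1.000 | 1.000 |

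**False significance at nominal 5%** (two-sided Chi2, 200,000 simulated tables per cell, 2% operated)

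| Surgery timing | 200 vs 9,800: 2 / 5 / 10 years | 1,000 vs 49,000: 2 / 5 / 10 years |
|---|---|---|
| 0–2 years | 19.3 / 9.7 / 7.3% | 87.4 / 40.3 / 21.3% |
| 0–1 year | 5.6 / 5.2 / 5.1% | 20.5 / 10.4 / 7.7% |
| 3–12 months | 7.3 / 5.9 / 5.5% | 35.4 / 15.4 / 9.7% |

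Equal timing gives about 5%.

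**Small gap.** With fixed treatment times, drugs at 0.5 months, surgery at 3 months and an assumed 5% two-year mortality, λ = −ln(0.95)/24 = 0.002137 per month. The risks are 1 − exp(−0.002137 × 21) = 0.0439 and 1 − exp(−0.002137 × 23.5) = 0.0490, a ratio of 0.90. Surgery at 6 or 12 months gives 0.77 or 0.52.

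**Direction.** If surgery falls in 0–1 year and drug-group entry in 0–2 years, the ratio is 1.49, 1.12 and 1.05 at 2, 5 and 10 years. This could arise if the yearly defined-daily-dose wording means that a patient needs accumulated use to count as drug-treated. With surgery in months 3–12, requiring survival to 6 months of drug use gives 0.92 at 2 years, and to 12 months 1.37.

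**Patients with both treatments.** If everyone starts drugs within three months and the 2% operated are counted as surgical, the 2-year ratios are 0.535, 0.800 and 0.733 for the three timings, almost unchanged. If patients are classified by first treatment, the ratio is about 1.0.

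**Spill-over to the treatment-type regressions.** Death before treatment also moves patients into the untreated category. With surgery over 0–2 years and drugs over 0–3 months, the surgical-versus-drug odds ratio for 8% versus 1% yearly mortality, from death alone, is (0.9241/0.9901)/(0.9901/0.9988) = 0.94. For 4% versus 1% it is (0.9610/0.9950)/(0.9901/0.9988) = 0.97.

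**The case against.** The strongest case against has three parts.

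First, the mechanism rests on premises that the documents do not state. The two-year periods are data-retrieval windows and are never said to define the groups; the start of mortality counting is open; no treatment timing is given. This stands, and the point is therefore conditional. But these are the only post-inclusion treatment windows in the plan, and no other rule is offered. Counting deaths from treatment would remove the guaranteed survival time, but the plan does not say so, and a fixed end at two years after inclusion would still leave unequal time at risk.

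Second, neither size nor direction is established. This also stands. A reader might infer that the test is bound to favour surgery. The documents do not support that: later surgery is plausible, since the Background stresses a thorough preoperative workup, but equal timing gives no bias and later drug-group membership reverses it.

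Third, the item is labelled descriptive. A Chi2 test on observed proportions validly compares observed deaths, and misleads only if read as a treatment effect. The plan proposes no such reading. This keeps the matter minor. It does not make the p-value informative, because a difference produced by group formation says nothing useful about either group.

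**Conclusion.** The concern holds conditionally and is minor. If the two-year windows define the groups, deaths count from inclusion and time to treatment differs, the planned mortality test is biased with no treatment effect present, and nothing else in the plan corrects it. The distortion could be negligible or large. It grows with cohort size and later surgery and shrinks with longer follow-up, but these need not all coincide: the large-cohort case still gives 40% false significance at 5 years with surgery spread over two years, and 35% at 2 years with surgery confined to months 3–12. In the smaller cohort, two of the three surgery timings give only about 5–7% at any horizon.

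A reader might also infer that the main analyses are compromised. The documents do not support that. The mortality comparison feeds no model. The treatment-type regressions share the survive-to-treatment rule, but the effect there is small (odds ratios of about 0.94–0.97 under strong mortality contrasts), so they are not materially affected. Confounding by age and comorbidity is a separate matter.

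**What to change.** Remove mortality from the items tested between drug-treated and surgically treated patients. Report deaths for the whole cohort and state the length of mortality follow-up.

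Only if a comparison is wanted, use one of these:
- Count deaths and person-time from inclusion, with treatment as a time-dependent exposure (untreated, drug, surgery). In a check under the same no-effect model, the rate ratio was 0.99–1.01.
- Use a landmark at two years, provided that mortality follow-up extends beyond two years. In a separate simulation (24-month landmark, deaths in the next 24 months), the risk ratio was 1.00–1.01 and rejection was 4.4–6.7%.

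Either way, state time zero, follow-up length and how patients with both treatments are classified in the analysis.

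The main change costs almost nothing: readers lose one unadjusted p-value. The optional comparison needs a little more Stata code on data already retrieved. The landmark discards deaths in the first two years, and confounding by indication remains under either option.

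### The equal-variance t-test is named for comparing drug-treated with surgical patients; if group sizes and age spreads both differ it is miscalibrated, and Welch's test avoids this at no cost

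*Combined protocol and SAP*

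**What the plan says.** The Statistical analysis section opens with a "Descriptive analysis of age, sex, Charlson Comorbidity Index, mortality and rate of anti-thrombotic treatment". The two groups set against each other are drug-treated and operated patients. The tests listed for this comparison are "Student's t-test, Chi2-test and Mann-Whitney-U test". The plan does not say which test goes with which variable, and it mentions neither equal nor unequal variances.

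Group sizes are not given. The Background section says that "it is currently unknown how many patients each year are given the diagnosis GERD after upper endoscopy in Denmark and what treatment they receive". The same section gives indirect indications of imbalance: in earlier Danish data "the rate of primary surgery was 5.2 per 100.000 inhabitants", in Denmark "the popularity of anti-reflux surgery has been somewhat limited", and the disease is described as "affecting 10-20% of the Western population". Under Methods, only anti-reflux operations within two years of inclusion are counted.

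The later analyses (logistic and multinomial regression as primary, then Cox and Poisson regression) do not use the t-test.

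**The concern.** Student's t-test pools the two variances, weighting each group by its size. When one group is much larger, the pooled variance is in effect that group's variance. The variance of the difference in means, however, is dominated by the smaller group. If the two spreads are the same, this does no harm. If they differ, the standard error is wrong by roughly the ratio of the two SDs, and enrolling more patients at the same ratio does not repair it.

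Both conditions are plausible here. Surgery looks uncommon, and the Background section links good surgical results to careful selection of patients, so the age spread of operated patients need not match that of everyone treated with drugs. At stake are the p-value for the age comparison and any confidence interval computed from the same standard error.

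**Working it through.** **Inputs.** The documents state no sample size, SD or significance level, so there is no figure of theirs to reproduce. From the documents: the test named, the two groups compared, and 5.2 primary operations per 100,000 inhabitants. Assumed: two-sided 5% level, the group sizes and the SDs below.

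**How small might the surgical group be?** With an assumed population of 4 to 6 million, 5.2 per 100,000 gives 208 to 312 operations a year. Over the 16 calendar years 2000-2015, that is 208 × 16 = 3,328 to 312 × 16 = 4,992 if the rate held. Only operations within two years of a new, endoscopy-supported diagnosis would count, so the surgical group would be smaller than this. The size of the drug group cannot be derived from the documents.

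**Formulas** (S = surgical, D = drug):
- Pooled variance: sp² = [(nS − 1)sS² + (nD − 1)sD²] / (nS + nD − 2)
- Pooled SE = sp × √(1/nS + 1/nD)
- Correct (Welch) SE = √(sS²/nS + sD²/nD)
- True size of the nominal 5% test = 2 × [1 − Φ(1.96 × pooled SE / correct SE)]

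**Main illustration**, sD = 17, sS = 13, nD = 80,000, nS = 1,500:
- sp² = (1,499 × 169 + 79,999 × 289) / 81,498 = 286.8, so sp = 16.94. This is almost the drug SD, because the surgical group has a weight of 1,499/81,498 = 1.8%.
- Pooled SE = 16.94 × √(1/1,500 + 1/80,000) = 0.441 years.
- Correct SE = √(169/1,500 + 289/80,000) = √(0.1127 + 0.0036) = 0.341 years. The surgical group supplies 0.1127/0.1163 = 97% of this variance.
- Ratio 0.441/0.341 = 1.29; true size 2 × [1 − Φ(2.54)] = 0.011.
- 95% half-widths: 0.865 years pooled, 0.668 years correct, a gap of 0.20 years. The 5% verdict changes only if the observed mean age difference lies between these two values.

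**Dependence on the assumptions:**

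| nD : nS | SD drug / surgical | Pooled SE / correct SE | True size |
|---|---|---|---|
| 80,000 : 1,500 | 17 / 13 | 1.29 | 0.011 |
| 80,000 : 1,500 | 16 / 14 | 1.14 | 0.026 |
| 10,000 : 1,000 | 17 / 13 | 1.24 | 0.015 |
| 5,000 : 1,000 | 17 / 13 | 1.19 | 0.019 |
| 1,000 : 1,000 | 17 / 13 | 1.00 | 0.050 |
| any | equal SDs | 1.00 | 0.050 |

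For SDs 16 and 14 at 80,000 : 1,500, the half-widths are 0.816 and 0.717 years, a gap of 0.10.

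**Welch under the same conditions.** In simulations of 4,000 normal data sets with 500 surgical and 10,000 drug patients, the pooled test rejected a true null in 1.7% of data sets when the surgical SD was 0.8 times the drug SD, and in 10.4% when it was 1.25 times. Welch rejected in 4.7% and 4.8%.

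**The case against.** The strongest reply is that the fault depends on quantities that the documents do not give. The 5.2 per 100,000 is a rate per inhabitant for 1997-2005, not the share of newly diagnosed patients who have surgery within two years, so it cannot fix the allocation ratio. No SD is stated, and with equal spreads or equal group sizes there is no error at all. This stands: the imbalance is a fair inference, and the unequal spread is only a possibility.

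A reader might infer that the plan's intervals will be too narrow. With a surgical SD 1.3 times the drug SD at 80,000 : 1,500, the SE ratio is 0.78 and coverage about 87%. The documents do not support that direction. Patient selection would more naturally narrow the surgical spread, which makes the pooled test conservative. The plan also promises no confidence intervals from this comparison.

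A reader might also infer that every variable in the descriptive table is affected. Sex, mortality and anti-thrombotic treatment suit the chi-square test, and the rank test is available for the Charlson index. Age is the only clear t-test variable.

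Finally, the name Student's t-test is often used loosely, and the plan never says that variances will be pooled. That is possible, but read literally the name means the equal-variance test. The Mann-Whitney test listed beside it does not remove the point: it gives no mean difference and is itself sensitive to unequal spreads.

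**Conclusion.** The point holds in a limited form, as a small improvement. The named test is the equal-variance one, the surgical group is likely to be much the smaller, and if the age spreads also differ the test will not have its nominal size. Under assumed SDs of 17 and 13, the pooled standard error is 19% too large at 5:1 and 29% too large at 80,000 : 1,500, with a true size between about 2% and 1%. In years the effect is small: 0.1 to 0.2 of half-width at 80,000 : 1,500 with the SDs tried. All of this rests on assumed sizes and spreads.

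It would be wrong to read this as a threat to the study's main results. The logistic, multinomial, Cox and Poisson models do not use the t-test and are unaffected.

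**What to change.** In the Statistical analysis section, replace Student's t-test by the unequal-variance (Welch) t-test for age and for any other variable that will be compared by means. Name those variables, and report the mean difference with its 95% CI.

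The cost is one option in the Stata command and one line of text. If the spreads turn out equal, Welch loses essentially nothing at sample sizes of this order; if they differ, it gives the correct standard error.

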Logistic and multinomial regression will be performed with treatment type (pharmacological, surgical or none) as primary outcome and age, sex, Charlson Comorbidity Index, pharmacological anti-reflux treatment prior to diagnosis, antithrombotic treatment and year of diagnosis as independent variables.

Secondary analysis will be performed using Cox-regression investigating time to initiation of any treatment with age, sex, Charlson Comorbidity Index, pharmacological anti-reflux treatment prior to diagnosis, antithrombotic treatment and year of diagnosis as independent variables. Change in treatment rates over time will also be investigated using national Danish census data and Poisson regression.

Sensitivity analysis excluded patients with anti-thrombotic treatment will be performed.

Funding and Ethical considerations

The study is part of a ph.d. thesis and is funded by The Region of Southern Denmark, The University of Southern Denmark, The Department of Surgery, Kolding Hospital and The Research Council at Little Belt Hospital.

The study requires no informed consent in Danish law as the study is register-based. However, permission from The Danish Data Protection Agency and The Danish Health Data Agency will be obtained before the study is commenced.

None of the involved parties have financial interests or conflicts of interest pertaining to this study.

References

1. Madanick RD. Extraesophageal presentations of GERD: where is the science? *Gastroenterol Clin North Am.* 2014;43:105-120.

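### Three unreconciled time anchors let an anti-reflux drug started between endoscopy and diagnosis be coded as prior treatment, and under one reading as outcome treatment too

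*Combined protocol and SAP*

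**What the plan says.** The combined protocol and SAP ties its dates to three different events.

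- **Endoscopy (Methods).** The study period: "Endoscopy must have been performed during the study period 2000-2015". The washout: "Patients with GERD and GERD-related diagnosis up to four years before upper endoscopy are excluded from the study". The baseline characteristics: "Age, sex and Charlson Comorbidity Index at date of primary upper endoscopy are derived" from the patient registry.
- **Inclusion (Methods), never defined.** Anti-reflux surgery is counted over two years from inclusion. Anti-reflux drug data "are identified from 4 years before inclusion to 2 years after".
- **Diagnosis (Statistical analysis).** The primary regression and the Cox model both use "pharmacological anti-reflux treatment prior to diagnosis, antithrombotic treatment and year of diagnosis as independent variables".

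The endoscopy and diagnosis dates can differ by design, since "upper endoscopy must have been performed no more than three months before time of diagnosis". The primary outcome is treatment type in three categories (drug, surgery, none). It has no stated start date and no rule separating new use from continued use. The Cox outcome is time to starting any treatment, and its time zero is not stated.

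**The concern.** The study asks what treatment patients receive once endoscopy has led to a GERD diagnosis. A drug begun because of the endoscopy, before the diagnosis is registered, belongs to that outcome. Under the stated covariate rule it is baseline use, because it was dispensed before diagnosis. Part of the outcome then enters a predictor of the same outcome.

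At stake are the prior-treatment coefficient in the primary model and the meaning of time to initiation in the Cox model. Prior drug use is likely to be one of the more strongly predictive covariates, so its estimate will be read and interpreted.

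**Working it through.** The plan states no figure to reproduce on this point. The check has three parts.

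**1. Where a first dispensing falls.** Let endoscopy be day 0 and diagnosis day g, with g between 0 and about 91 (three months). A first dispensing on day s, with 0 ≤ s < g, is always before diagnosis and so always prior treatment. The outcome side depends on what inclusion means:

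| Inclusion date | Same dispensing in the two-year outcome window? | Overlap at g = 0 / 30 / 91 | Cox model |
|---|---|---|---|
| Endoscopy | Yes | 0 / 30 / 91 days | If time zero is endoscopy, the covariate uses information from after it |
| Diagnosis | No | 0 / 0 / 0 days | If time zero is diagnosis, the start precedes it; no rule says how to handle this |

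The maximum overlap is 3 of 24 months, or 12.5% of the window. In the second row, refills after diagnosis still make the patient drug-treated, because there is no new-use rule. The two-year drug outcome window is itself inferred from the data-retrieval sentence.

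**2. Effect on the prior-use odds ratio.** All inputs are assumptions; none is in the documents. Per 100 patients: 50 true prior users, of whom 85% are treated (42.5 treated, 7.5 not); 50 non-users, of whom 60% start (30 treated, 20 not).

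True odds ratio = (42.5/7.5) / (30/20) = 3.78.

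If a share f of the 30 new starters is relabelled as prior users and still counted as treated, the odds ratio is ((42.5 + 30f)/7.5) / ((30 − 30f)/20). Take f as the share of patients with a gap times the share of their starts that fall in it. With 10-20% and 50-80%, f runs from 0.10 × 0.50 = 5% to 0.20 × 0.80 = 16%.

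- f = 5%: (44.0/7.5) / (28.5/20) = 4.12
- f = 8%: (44.9/7.5) / (27.6/20) = 4.34
- f = 10%: (45.5/7.5) / (27.0/20) = 4.49
- f = 16%: (47.3/7.5) / (25.2/20) = 5.01

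A second illustration sets the true odds ratio to 1, with 30-50% true prior users and 60-80% treated. The apparent odds ratio is 1.13-1.30 if 5% of all non-users start in the gap, and 1.29-1.67 if 10% do. For example, with 30% prior users, 60% treated and 5% starting in the gap:

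- observed prior users: 0.30 + 0.70 × 0.05 = 0.335
- treated among them: (0.18 + 0.035)/0.335 = 0.642
- treated among the rest: (0.60 − 0.05)/0.95 = 0.579
- odds ratio: 1.30

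**3. Effect on another covariate.** A two-period calendar variable was added to the first illustration and a logistic model fitted with 5-16% relabelled.

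- Prior use 50% in both periods: true period odds ratios of 1.00, 1.30 and 1.50 are essentially unchanged (at most 1.505 for 1.50).
- Prior use 40% then 60%: 1.00 becomes 0.99-0.97, 1.30 becomes 1.29-1.26, and 1.50 becomes 1.49-1.46.

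**The case against.** The strongest defence is that the plan is loosely worded rather than wrong. Most Methods anchors are at endoscopy, and the single drug window divides naturally at inclusion into lookback and follow-up. If prior to diagnosis is shorthand for that lookback, nothing overlaps. That may be the intention, but the text does not say so, and the rule as stated codes gap starts as prior use whichever date inclusion is.

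The defence succeeds against several stronger readings that a reader might infer:

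- *Gap dispensings are necessarily counted twice.* This needs inclusion to be the endoscopy date. Under a diagnosis date no single dispensing is on both sides, and patients with same-day endoscopy and diagnosis are unaffected under either.
- *Under a diagnosis date, the new start drops out of the outcome.* That holds for the initiation event but not for treatment type, since refills after diagnosis still count. The inflation in the illustration then depends on patients refilling; a patient who never refills and has no surgery would be coded as a prior user with no treatment, which pulls the other way.
- *All adjusted effects, or the 15-year comparison, are materially biased.* In the check above, other effects move little. They could move more if gap length changed over calendar time, but the documents give no sign of this. The census-based Poisson analysis does not rest on the prior-use coefficient.
- *The bias is known to be large.* Three months is an eligibility maximum, not a typical gap. Relabelling of 32% would give an odds ratio of 6.81, but nothing in the documents supports that scenario.

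Diagnosis is also a defensible index for a cohort described as newly diagnosed. That argues for a sensitivity analysis, not for leaving the term undefined.

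**Conclusion.** The point holds in a limited form and should be corrected before analysis. An anti-reflux drug first dispensed between endoscopy and diagnosis is coded as prior treatment under either meaning of inclusion. Same-dispensing double counting, for up to about 91 days, arises only if inclusion is the endoscopy date. The Cox model is affected either way: the covariate looks past time zero, or the initiation falls before it.

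The expected consequences are an inflated prior-use coefficient and a distorted time to initiation. Bias in other adjusted effects is possible but probably small. The rise from 3.78 to 4.1-5.0 is illustrative. It rests on assumed rates of prior use, treatment and gap starts, and on a treated/untreated simplification of a three-category outcome. The Cox distortion has not been quantified. The true size cannot be stated from the documents.

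**What to change.** Define inclusion as the date of the primary upper endoscopy. Count prior treatment only from dispensings strictly before that date. Start the two-year surgical and drug outcome windows and the Cox time origin on it. With one boundary, the overlap is zero days. State also how patients who continue earlier drug treatment are classified in the outcome and in the Cox model.

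There is a small downside. Patients must survive from endoscopy to diagnosis, at most three months, to enter the cohort, and this conditions every analysis with an endoscopy origin, not only mortality. So measure mortality from diagnosis, and repeat the treatment-type and Cox analyses with diagnosis as origin, keeping prior use defined before endoscopy, as a sensitivity analysis. It would also help to report the distribution of the endoscopy-to-diagnosis gap by calendar year, which would show how much this matters.

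The cost is a few sentences in the plan, a change of date variable and one extra set of model runs. No new data are needed, because the registry dates and prescriptions are already being retrieved.

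### The secondary Cox model appears to pool drug starts with surgery, so its hazard ratios would describe almost entirely drug starts; separate models by treatment would make it informative about surgery

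*Combined protocol and SAP*

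**What the plan says.** The Aim is "To compare rate of surgery with medical treatment in patients with newly diagnosed gastro-esophageal reflux disease".

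The Statistical analysis section serves it with several analyses. The primary one is "Logistic and multinomial regression will be performed with treatment type (pharmacological, surgical or none) as primary outcome", and its covariates are age, sex, Charlson index, "pharmacological anti-reflux treatment prior to diagnosis, antithrombotic treatment and year of diagnosis as independent variables". The secondary time-to-event analysis follows: "Secondary analysis will be performed using Cox-regression investigating time to initiation of any treatment with age, sex, Charlson Comorbidity Index" and the other three of the same six covariates. The section then adds "Change in treatment rates over time will also be investigated using national Danish census data and Poisson regression".

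On data, the Methods section says that operations "performed within two years of inclusion are identified", and that antacid and anti-secretory drugs (MA02B) "are identified from 4 years before inclusion to 2 years after". Patients already using these drugs are not excluded; earlier use is a covariate. Mortality during follow-up is also retrieved.

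The plan contains no time-to-surgery analysis, cause-specific hazard model or cumulative incidence by treatment. It does not say how the Cox event combines the two treatments, what initiation means for a patient already on these drugs, or how death is handled in the Cox model.

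**The concern.** The Aim contrasts surgery with medical treatment, but the only model that uses time merges the two into one event. Take a patient who fills a prescription shortly after endoscopy and is operated on ten months later. In this model the event occurs at the first dispensing, and the operation plays no further part. Only an operation that precedes any dispensing in follow-up counts as a surgical event.

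The two treatments may also have different, even opposite, predictors. A single hazard ratio for age, Charlson index or year of diagnosis averages over them, weighted by how often each comes first. If drugs nearly always come first, the hazard ratio is in effect the one for drug starts. Set beside the primary results, it could be mistaken for evidence about choice of treatment.

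**Working it through.** The plan states no sample size, event count, uptake or hazard ratio, so there is no figure of its own to reproduce. What follows is an illustration on assumed inputs.

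**Assumed inputs (not in the documents).** Two-year drug uptake p_d is 60-90% and two-year surgery uptake p_s is 1-5%. The two-year horizon is the plan's own follow-up.

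**Step 1: share of first events that are surgical.** Assume constant hazards, with each treatment equally free to come first, and treat each uptake as what would be seen if the other treatment did not intervene. Then h = -ln(1 - p)/2 per year, and the surgical share is h_s/(h_d + h_s).

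- p_d = 0.90, p_s = 0.01: h_d = 1.1513, h_s = 0.00503; share = 0.00503/1.1563 = 0.0043, or 0.4%.
- p_d = 0.60, p_s = 0.05: h_d = 0.4581, h_s = 0.02565; share = 0.02565/0.4838 = 0.053, or 5.3%.

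**Step 2: allow for drugs usually coming first.** Work with proportions instead. Let d be the proportion starting a drug, s the proportion operated on, and f the fraction of operated patients with an earlier dispensing. The share is s(1 - f)/[s(1 - f) + d].

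- d = 0.60, s = 0.05, f = 0: 0.05/0.65 = 7.7%.
- d = 0.60, s = 0.05, f = 0.5: 0.025/0.625 = 4.0%.
- d = 0.60, s = 0.05, f = 0.9: 0.005/0.605 = 0.8%.
- d = 0.90, s = 0.01, f = 0.9: 0.001/0.901 = 0.1%.

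The two formulas differ somewhat at the upper end (5.3% against 7.7%). Under either, drug starts make up at least about 92% of first events.

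**Step 3: effect on the pooled hazard ratio.** The pooled HR is about (1 - share) × HR_drug + share × HR_surgery.

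- A covariate that doubles the surgery hazard and leaves drugs unchanged gives 1 + share. With the shares in Step 2, that is 1.001 to 1.08.
- A covariate that halves the surgery hazard (0.5) and raises the drug hazard by 20% (1.2) gives 1.2 - 0.7 × share. With the shares in Step 1, that is 1.2 - 0.7 × 0.053 = 1.16 to 1.2 - 0.7 × 0.0043 = 1.20.

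In both cases the effect on surgery leaves almost no trace in the pooled figure.

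**Step 4: what the other analyses cover.** The primary model keeps surgical treatment as its own category and uses the same six covariates, so it estimates predictors of surgery over the two years. The descriptive comparison separates drug-treated from operated patients, and the Poisson analysis covers change in treatment rates. None of these gives an individual patient's time to operation.

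**The case against.** The strongest reply is that the study already answers its question elsewhere. A reader might infer from the Cox model that the plan says nothing about predictors of surgery, or that a deterrent effect of comorbidity on surgery would go unseen. The documents do not support that: the primary logistic and multinomial analysis has surgery as a separate outcome with Charlson index among its covariates. Nor is the patient operated on at ten months lost to the study. Operations within two years are identified, and the descriptive surgical group takes in any anti-reflux procedure. How a patient with both treatments is coded in the multinomial outcome is not stated, but that is a separate matter.

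It is also fair to say that the Aim speaks of rates and does not mention timing, and that time to first treatment of any kind is a legitimate description. A hazard ratio near 1.2 in the second example of Step 3 would be a correct answer to the question that model asks. The opposing directions there come from the hazard ratios chosen for illustration.

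A further tempting reading is that the model reports drug starts only. That is too strong. An operation that comes first would count as an event, and how rarely this happens rests on uptake figures that the plan does not give.

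All of these replies stand. Two things remain. The only model that uses time cannot, under plausible uptake, distinguish the treatments that the study contrasts. Its event is also under-defined, most clearly for patients already taking these drugs.

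**Conclusion.** The concern holds as a limitation of one secondary analysis. On its natural reading the Cox endpoint pools drug dispensing with surgery. With assumed two-year uptake of 60-90% for drugs and 1-5% for surgery, and constant hazards, surgery would be about 0.4-5.3% of first events, and fewer if most operated patients fill a prescription first. The hazard ratios would then reflect almost entirely drug starts, and this model could not show when surgery happens or what affects it.

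The plan does not fail to address its question, since the primary model estimates predictors of surgery within two years. The conclusion rests on the pooled reading of the endpoint and on the assumed uptake. Were surgery much more common as a first treatment than assumed, the dilution would be smaller, but the pooled model would still give one hazard ratio for two different treatments.

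**What to change.** Define the Cox event in the Statistical analysis section and add two cause-specific Cox models with the six covariates already listed. The pooled endpoint can stay as a descriptive summary.

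- **Model (a), surgery:** time from the index date to first anti-reflux operation, with follow-up continuing through drug dispensings and censoring at death.
- **Model (b), drugs:** time from the index date to first MA02B dispensing after it, censored at surgery and at death. State a rule for prior users, for example stratifying by prior use or restricting to non-users.
- **Cumulative incidence:** show the two-year cumulative incidence of each treatment with death as a competing event. In the drug curve, treat surgery as a competing event too.

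The cost is a few sentences and one model more than planned, or two if the pooled model is also kept, on dates already being retrieved. The drawback is that the surgery model will have fewer events and wider intervals.
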